### **8.4 Electronic Case Report Forms and Data Verification**

Subject data required by this protocol are to be transferred from the source to the eCRFs. The Investigator and his/her study site personnel will be responsible for completing the eCRFs. The Investigator is required to verify that all of the requested information is accurately recorded on the eCRFs. All information required on the eCRFs needs to be supplied, including subject identification, date(s), assessment values, etc., and any omission or discrepancy will require explanation. All information on eCRFs must be traceable to source documents. Market research data will be collected via ePRO and processed according to the policies and procedures of the ePro vendor. The data will not be included on eCRFs or verified by Bausch + Lomb.

A Clinical Monitor will be responsible for reviewing and verifying 100% of the data recorded on the eCRFs, utilizing the original source documentation, and will query discrepant findings. The Investigator and study site personnel will be responsible for answering all queries.

The eCRF data will be reviewed for completeness, accuracy, consistency, and medical sense. Programmed edit checks will be used to reduce data entry errors and identify unusual data for verification prior to statistical analysis.

A copy of the eCRF data will be retained at the conclusion of the study by the Investigator, who must ensure that it is stored in a secure place.

## **8.5 Recording of Data and Retention of Documents**

Subject data recorded on eCRFs during the study will be documented to maintain subject confidentiality. The subject will only be identified by the subject ID number. Confidentiality of subject's records must be maintained to ensure adherence to applicable local privacy regulations.

The Investigators have to retain records for 2 years after the investigational product is approved by the FDA. The Investigator agrees to adhere to the document retention procedures when signing the protocol Investigator Statement of Approval.

Essential documents include but are not limited to the following:

- Device Investigator Agreement
- Institutional Review Board approvals for the study protocol, all amendments, ICF(s), and advertisements
- Institutional Review Board annual study review
- Institutional Review Board correspondence and reports (e.g., AE reports, protocol deviations, and safety updates)
- Regulatory documents (e.g., financial disclosure and delegation of authority forms or records)
- All source documents
- Electronic CRFs
- Subject's signed ICF (including HIPAA)
- Accountability records for the test article(s)
- Correspondence from and to the Sponsor
- Any other documents relevant to the conduct of the study

In the event that study records are transferred to another location, the Investigator will provide notice of such transfer in writing to Bausch + Lomb Clinical Operations.

## **8.6 Auditing Procedures**

Audits of clinical research activities in accordance with the Sponsor's internal Standard Operating Procedures to evaluate compliance with the principles of GCP may take place. A regulatory authority may also wish to conduct an inspection (during the study or after its completion). If an inspection is requested by a regulatory authority and/or IRB, the Investigator must inform the Sponsor immediately that this request has been made.

## **8.7 Institutional Review Board**

The Investigator should ensure that the following are approved by their institution's IRB, or if not using their institution's IRB, approved by the reviewing central IRB prior to entering any subjects in the study:

- The protocol
- The Investigator's participation in the study
- Subject recruitment materials (written information or materials including web pages, radio advertisements, television spots, or written text developed to encourage subject enrollment)
- The ICF to be used in this study

Documentation of IRB approval of the study protocol and informed consent must be provided to the Sponsor prior to initiation of the study. In addition, the Investigator must ensure that the reviewing IRB has provided approval for any protocol amendments prior to implementation. If the amendment necessitates a revision to the ICF, the Investigator should ensure the revised form is also submitted to and approved by the Sponsor and the IRB and implemented as directed.

## **8.8 Publication of Results**

All study data generated as a result of this study will be regarded as confidential, until appropriate analysis and review by the Sponsor or its designee and the Investigator(s) are completed. The results of the study may be published or presented by the Investigator(s) after review by, and in consultation and agreement with, the Sponsor, and such that confidential or proprietary information is not disclosed.

Prior to publication or presentation, a copy of the final text should be forwarded by the Investigator(s) to the Sponsor or its designee, for comment. Such comments shall aim to ensure the scientific integrity of the proposed publications and/or presentations and ensure that the data and material referring to Bausch + Lomb products and activities receive fair, accurate, and reasonable presentation.

**APPENDIX A: SCHEDULE OF VISITS AND PARAMETERS**

All study tasks should be performed by qualified study site personnel as indicated on the delegation of authority log under the supervision of the Principal Investigator. **(Refer to important footnotes at the bottom of the table)**

PROCEDURE/ASSESSMENTS	Screening/ Dispensing Visit Day 1	1-Week Follow-Up Visit Day 8	3-Week Follow-Up Visit Day 23	Unscheduled Visit	Exit Visit
		Day 6-10 (5-9 days after V1)	Day 20-26 (19-25 days after V1)		
Informed consent/HIPAA authorization	X				
Demographics	X				
Contact lens use history and contact lens use (e.g., average daily wear time, number of days worn, lens brand, lens wear modality, lens care system brand, product use history)	X (Habitual)	X a	X a		
Ocular medical history and concomitant medications	X				
Changes in ocular medical history and concomitant medications		X	X	X	X
Eligibility	X				
Lens fitting	X	X b			
Dispense study materials	X	X		X b	
Collect worn /unworn lenses, blister foils and study materials		X	X	X	X
Adverse events	X	X	X	X	X
Symptoms/Complaints Form	X (Habitual)	X	X	X	
Subject-completed forms/surveys					
Baseline Questionnaire	X				
Lens Performance Rating Scales (after 10 minutes of lens settling & adaptation, if just inserted)	X c	X	X		
Instruct subject to complete Online Consumer Survey at least 7 days after the 1- Week Follow-Up Visit but before the 3-Week Follow-Up Visit		X			
Confirm Visit in ePRO (triggers survey and reminders)		X			
Confirm Subject has completed survey e			X		
With habitual lenses					
High-contrast distance logMAR lens VA(OU)	X				
Intermediate lens VA (OU)	X				
Near lens VA (OU)	X				
Without lenses					
Spherocylindrical refraction	X				X

PROCEDURE/ASSESSMENTS	Screening/ Dispensing Visit Day 1	1-Week Follow-Up Visit Day 8	3-Week Follow-Up Visit Day 23	Unscheduled Visit	Exit Visit
Near add power	X				
High-contrast distance logMAR BSCVA (OD/OS/OU)	X				X
High-contrast intermediate logMAR BSCVA (OU w/near add)	X				
High-contrast near logMAR BSCVA (OU w/near add)	X				
Pupil measurement	X				
Keratometry	X				X
Slit lamp exam	X	X	X	X	
With dispensed study lenses/With WORN study lensesd					
High-contrast distance logMAR lens VA (OU)	X	X	X	X	X
High-contrast intermediate logMAR lens VA (OU)	X	X	X	X	X
High-contrast near logMAR lens VA (OU)	X	X	X	X	X
Lens wettability	X	X	X	X	X

A large black rectangular redaction box is positioned at the top of the page. Below it, a smaller black rectangular redaction box is located at the bottom. To the right of these, there is a vertical column of black rectangular redaction boxes, with approximately seven boxes stacked vertically. The redaction boxes are solid black and completely obscure the underlying content.

A horizontal bar chart consisting of 10 bars of increasing length from left to right. The bars are solid black and are set against a white background. The first bar is the shortest, and the 10th bar is the longest, extending almost to the right edge of the frame.

A 2x10 grid of 20 black bars representing data series. The bars are of varying lengths and are positioned in two rows of ten. The top row has bars of lengths approximately 10, 15, 20, 10, 15, 20, 10, 15, 20, 25. The bottom row has bars of lengths approximately 20, 20, 20, 20, 20, 20, 20, 20, 20, 20.

The figure consists of 12 horizontal bar charts, each representing a state. The bars are black and the chart area is white. The length of each bar corresponds to the percentage of the population aged 65 and older in that state. The states are arranged vertically from top to bottom: California, Florida, New York, Texas, Massachusetts, Michigan, Ohio, Pennsylvania, Illinois, Indiana, Missouri, and North Carolina. The bars for California, Florida, and Texas are the longest, indicating the highest percentages of the population aged 65 and older in these states.

A bar chart with 15 categories on the y-axis. The x-axis is labeled from 0 to 100 in increments of 20. Category 15 is a large rectangle extending from approximately 10 to 90. Categories 1, 2, 3, 4, 5, 6, 7, 8, 9, 10, 11, 12, 13, and 14 are represented by shorter black bars. Category 1 is at 0, 2 is at 20, 3 is at 40, 4 is at 60, 5 is at 80, 6 is at 90, 7 is at 95, 8 is at 98, 9 is at 99, 10 is at 100, 11 is at 100, 12 is at 100, 13 is at 100, 14 is at 100, and 15 is at 100.

A 2D grayscale image showing a complex scene. The background is white. There are several black rectangular objects of various sizes and positions. Some rectangles overlap, and some are partially cut off by the image boundaries. The overall appearance is abstract and geometric.

A horizontal bar chart consisting of 10 bars. The bars are black and are arranged in a descending order of length from left to right. The first bar is the longest, and the tenth bar is the shortest. The bars are separated by small gaps.

A horizontal bar chart consisting of 20 black bars of varying lengths. The bars are arranged in two main groups: a top group of 10 bars and a bottom group of 10 bars. The bars in the top group are generally longer than those in the bottom group. The bars are set against a white background with no grid lines.

A 5x5 grid of horizontal black bars. The bars are of varying lengths, creating a visual pattern. The lengths of the bars in each row are approximately: Row 1: 10, 15, 20, 10, 10; Row 2: 10, 15, 20, 25, 30; Row 3: 30, 30, 30, 30, 30; Row 4: 10, 30, 30, 30, 30; Row 5: 10, 30, 30, 10, 30.

[REDACTED] [REDACTED]

100% of the time, the *hedgehog* is a hedgehog, and the *cat* is a cat.

For more information, contact the Office of the Vice President for Research and the Office of the Vice President for Student Affairs.

— 1 —

11. **What is the primary purpose of the *Journal of Clinical Endocrinology and Metabolism*?**

[REDACTED]

[REDACTED]

1000

11. **What is the primary purpose of the following statement?**

[REDACTED]

[REDACTED]

— 1 —

11. **What is the primary purpose of the *Journal of Clinical Endocrinology and Metabolism*?**

11. **What is the primary purpose of the *Journal of Clinical Endocrinology and Metabolism*?**

[REDACTED]

## APPENDIX C: SUBJECT INSTRUCTIONS

### **FOR SINGLE-USE DISPOSABLE WEAR**

**CAUTION: Investigational Device. Limited by Federal law (U.S.A.) to investigational use.**

#### **INTRODUCTION**

You will participate in this study designed to evaluate the product performance of the investigational Bausch + Lomb (kalifilcon A) Daily Disposable Multifocal Contact Lens (Test). Study lenses will be dispensed at the Screening/Dispensing Visit. **It is very important that you do not use any other contact lenses other than those dispensed to you during the study.**

You will wear the lenses on a daily disposable basis and replace the lenses daily but **do not discard your worn lenses**, as they will be collected at your 1-Week and 3-Week Follow-Up Visits. Throughout the study, place all worn lenses in a study lens case that was provided to you (up to 10 pairs of lenses per case) with no solution (dry). You will return the lens cases to the office at your 1-Week and 3-Week Follow-Up Visits/Exit Visit. Bring all lenses (worn in lens cases and unworn blister packs) and blister foils to the 1-Week and 3-Week Follow-Up Visits/Exit Visit or any unscheduled visit.

Please keep all appointments and follow these instructions thoroughly. If you have any questions or problems, call your study doctor at \_\_\_\_\_.

***Note: Please schedule your 1-Week and 3-Week Follow-up Visits at the Screening/Dispensing Visit.***

#### **Follow-Up Visit Schedule**

Visit	Day	Month	Year	Time
1-Week Follow-Up	/	/		
*At the 1-Week Follow-up, you will be provided information regarding an Online Consumer Survey to be completed after at least 7 days of wear after the 1-Week Follow-Up Visit but before the 3-Week Follow-Up Visit.				
3-Week Follow-Up	/	/		

***Note: Wear your study lenses to your follow-up visit.***

For this study, you will be using the following products:

- Lens cases for storage of worn study lenses (up to 10 pairs of lenses, stacked dry).

#### **GENERAL INFORMATION**

***Do NOT use any products other than those dispensed to you by your study doctor for use in this study, with the exception of rewetting drops if you habitually use them.***

If problems or symptoms should occur, immediately remove your lenses, and follow the steps described in the sections of these instructions entitled **Warnings** and **Adverse Effects**. Prompt attention to problems is essential and may require immediate professional care.

Remember, when wearing contact lenses, your eyes should look and feel good, and your vision should be clear.

Because they are worn directly on your eyes, contact lenses affect the way in which your eyes function. These effects tend to increase with the length of time the lenses remain on your eyes between removals. Although the great majority of people successfully wear contact lenses without problems, before you decide whether to continue wearing contact lenses for daily disposable wear, you should discuss with your study doctor the effects of contact lenses on your eyes and the risks associated with wearing contact lenses. You also should read the sections of these instructions entitled "Warnings", "Adverse Reactions", "Precautions", and "Wearing Restrictions and Indications". Ask your study doctor to explain anything that you do not understand, including any additional restrictions which may be given to you by your study doctor. These contact lenses have been prescribed for single-use disposable wear and should be replaced each time lenses are removed from your eyes.

You also need to remember that soft contact lenses, including those covered by these instructions, are made of a type of plastic that absorbs liquids, vapors, and small particles, and for some people, may collect deposits from your natural eye fluids. Therefore, you should strictly follow these instructions and any other instructions given to you by your study doctor. Any failure to follow these instructions and the wearing restrictions will increase the chances of contamination, damage to the lenses, or a buildup of deposits on the lenses, which can lead to serious, sight-threatening eye infections and injuries.

Adherence to your prescribed wearing schedule and regular check-up visits to your study doctor are also necessary for the proper and safe use of contact lenses. Soft contact lenses generally are comfortable from the beginning. Therefore, be sure to follow the wearing schedule prescribed for you, and do not over wear your lenses simply because they remain comfortable, and you are not experiencing a problem. Only your study doctor, through a professional examination, can determine how your eyes are reacting to the contact lenses and whether there are any early signs of possible problems.

Finally, if problems or symptoms should occur, immediately remove your lenses, and follow the steps described in the section of these instructions entitled "Warnings and Adverse Reactions." Prompt attention to problems is essential and may require immediately professional care.

Remember, when wearing soft contact lenses your eyes should look and feel good, and your vision should be clear.

## **1. WEARING RESTRICTIONS and INDICATIONS**

The lenses have been prescribed for single-use disposal wear and will be replaced after each removal.

- Keep a spare pair of lenses and a lens case available in case you have to remove your lenses immediately upon the appearance of a problem or symptom.
- Do not use aerosol products such as hair spray while wearing your lenses. The lenses may absorb the spray, resulting in injury to the eye and damage to the lens.
- Avoid wearing the lenses around fumes, irritating vapors, smoky or dusty conditions. The lenses may absorb the chemicals or particles, resulting in injury to the eye.
- Avoid rubbing your eyes with the lenses in, which can irritate the eye or dislodge the lens.

- If you get something in your eye, remove the lens immediately. Do not replace with new lens until your eye feels normal.
- Tell your regular physician and every other doctor that you visit, that you wear contact lenses and the type of lenses that you wear. If you are admitted to a hospital, also tell your nurses that you wear contact lenses.
- Do not use any eye drops, ointments, or medicines in your eye unless they are specifically approved by your study doctor or physician. Some drops, ointments, or medicines will cause injury to the eye if used by a contact lens wearer.
- Ask your study doctor whether there are any other wearing restrictions that apply to you, write those restrictions in the spaces provided below and follow them carefully.

---

---

---

---

## 2. WARNINGS

You should be aware of and fully discuss with your study doctor the following warnings pertaining to contact lens wear:

- Problems with contact lenses could result in serious injury to your eye. It is essential that you follow your study doctor's direction and all labeling instructions for proper use of lenses. Eye problems, including corneal ulcers, can develop rapidly and lead to loss of vision.
- Daily disposable lenses are not indicated for overnight wear, and you should not wear lenses while sleeping. Clinical studies have shown that the risk of serious adverse reactions is increased when daily disposable lenses are worn overnight.
- Strict compliance with your wearing restrictions, wearing schedule, and follow-up visit schedule should be followed.
- Studies have shown that contact lens wearers who are smokers have a higher incidence of adverse reactions than nonsmokers.
- If you experience eye discomfort, excessive tearing, vision changes, or redness of the eye, you should immediately remove lenses and promptly contact your study doctor.

## 3. PRECAUTIONS

You should be aware of and fully discuss with your study doctor the following safety precautions:

- Do not use saliva or anything other than the recommended solutions for lubricating or wetting your lenses.
- If the lens sticks (stops moving), you should use a solution intended to lubricate or rewet a contact lens, as recommended by your eyecare practitioner. The lens should move freely on your eye for the continued health of your eye. If non-movement of the lens continues, you should immediately consult your study doctor. Do not attempt to remove the lens, except on the instructions of your study doctor.

- Always wash and rinse your hands before handling lenses. Do not get cosmetics, lotions, soaps, creams, deodorants, or sprays in your eyes or on the lenses. It is best to put on lenses before putting on makeup. Water-base cosmetics are less likely to damage lenses than oil-base products.
- Do not touch contact lenses with your fingers or hands if your hands are not free of foreign materials, as microscopic scratches of the lenses may occur, causing distorted vision and/or injury to your eye.
- Carefully follow these handling, insertion, and wearing instructions for the daily disposable contact lenses and those instructions prescribed by your study doctor.
- Never wear lenses beyond the period recommended by your study doctor.
- Always handle lenses gently and avoid dropping them.
- Ask your study doctor about wearing lenses during water activities and other sports.
- Inform your doctor (health care professional) about being a contact lens wearer.
- Never use tweezers or other tools to remove lenses from the lens container unless specifically indicated for that use. Pour the lens into your hand.
- Do not touch the lens with your fingernails.
- Always contact your study doctor before using any medicine in your eyes.
- Always inform your employer of being a contact lens wearer. Some jobs may require use of eye protection equipment or may require that you not wear contact lenses.
- As with any contact lens, follow-up visits are necessary to assure the continuing health of your eyes. Your study doctor should provide you with a recommended follow-up schedule.

#### **4. ADVERSE REACTIONS (Problems and What to Do)**

You should be aware that the following problems may occur:

- Eyes stinging, burning, itching (irritation), or other eye pain,
- Comfort is less than when lens was first placed on eye,
- Abnormal feeling of something in the eye (foreign body, scratched area),
- Excessive watering (tearing) of the eyes,
- Unusual eye secretions,
- Redness of the eyes,
- Reduced sharpness of vision (poor visual acuity),
- Blurred vision, rainbows, or halos around objects,
- Sensitivity to light (photophobia),
- Dry eyes.

If you notice any of the above, you should:

- Immediately remove your lenses.

- If the discomfort or problem stops, then look closely at the lens. If the lens has dirt, an eyelash, or other foreign body on it, or the problem stops and the lens appears undamaged, insert a new lens. After insertion of a new lens, if the problem continues, you should immediately remove the lenses and consult your study doctor.

When any of the above problems occur, a serious condition such as infection, corneal ulcer, neovascularization, or iritis may be present. You should keep the lens off your eye and seek immediately professional identification of the problem and prompt treatment to avoid serious eye damage.

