***Note: All VA measurements MUST be made using a phoropter.***

- a. Collect changes in ocular medical history and concomitant medications
- b. Collect the following study lens information from the subject:
  - Over the last week, Average number of days per week worn
  - Over the last week, Average daily wearing time, hours per day
  - Over the last week, Average hours of comfortable wear per day
  - Hours lenses worn on the day of this visit
  - Over the last week, average number of times used rewetting drops per day. (Note: Only to be completed by subjects reporting rewetting drop use with habitual lenses at the Dispensing Visit.)
- c. Collect the Lens Performance Ratings for dispensed contact lenses using the 0-100 rating scales provided by the Sponsor.
- d. Collect the Symptoms/Complaints for dispensed lenses.
- e. If the subject did not come to the visit wearing one or more study lenses, go to step g. Otherwise, evaluate the study lenses (while on eye) and record the following assessments:
  - Distance (OU), intermediate (OU), and near (OU) lens VA
  - Lens wettability
  - Lens deposits (type, percent, and degree)

- Lens centration
- Lens movement

Compare the high-contrast OU distance lens VA to the high-contrast OU distance BSCVA obtained at the Screening/Dispensing visit. If the VA has decreased by  $\geq 10$  letters, explain.

f. If the subject requires a change to their study lens power at the 1-Week Follow-Up Visit, collect the worn lenses from the subject, and the unworn lenses for the eye(s) requiring a change, adjust the lens power, dispense study lenses with the appropriate power according to the Fitting Guide, and perform assessment in step e, (with exception of deposits), after an equilibration time of 10 minutes.

***Note: Study lenses should be allowed to equilibrate a minimum of 10 minutes on the eye. Subjects should be encouraged to walk around, read, and/or look outside while the lens is equilibrating. If the first set of study lenses is unacceptable to the subject, adjust study lenses according to the Fitting Guide to achieve acceptable vision. Continue to adjust until vision is acceptable. Allow the study lens(es) to equilibrate a minimum of 10 minutes on the eye before conducting the assessments in step e. Number of refinements completed to achieve satisfactory vision in each eye will need to be collected.***

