#### **– Removing the Lens:**

Always remove the same lens first.

- 1) Always wash your hands thoroughly with mild soap, rinse completely, and dry with a lint-free towel before touching your lenses.

2) Always be sure that the lens is in the correct position on your eye before you try to remove it (a simple check of your vision, closing one eye at a time, will tell you if the lens is in the correct position). Look up and slowly pull down your lower eyelid with the middle finger of your removal hand and place your index finger on the lower edge of lens. Squeeze the lens lightly between the thumb and the index finger and remove it. Avoid sticking the edges of the lens together.

3) Remove the other lens by following the same procedure.

***Note: If this method of removing your lens is difficult for you, your study doctor will provide you with an alternate method.***

– **Care for a Sticking (Nonmoving) Lens:**

It is important to the health of your eyes that your contact lenses move freely. If a lens sticks (stops moving), use a solution intended to lubricate or rewet a contact lens, as recommended by your eyecare practitioner. In this case, do not use plain water or anything other than the recommended solutions. Do not attempt to remove a lens that is sticking, which could damage your eye. If the lens does not begin to move when you blink after several applications of the solution or, contact your study doctor immediately. Do not attempt to remove the lens except on the advice of your study doctor.

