## WARNINGS

After a thorough eye examination, including appropriate medical background, subjects should be fully apprised by the prescribing professional of all the risks with contact lens wear. Subjects should be advised of the following warnings pertaining to contact lens wear:

- Problems with contact lenses could result in **serious injury** to the eye. It is essential that subjects follow their eye care professional's direction and all labeling instructions for proper use of lenses. Eye problems, including corneal ulcers, can develop rapidly and lead to **loss of vision**.
- Daily disposable lenses are not indicated for overnight wear, **and subjects should be instructed not to wear lenses while sleeping**. Clinical studies have shown that the risk of serious adverse reactions is increased when daily disposable lenses are worn overnight.
- Studies have shown that contact lens wearers who are smokers have a higher incidence of adverse reactions than nonsmokers.
- If a subject experiences eye discomfort, excessive tearing, vision changes, or redness of the eye, the subject should be instructed to **immediately remove lenses** and promptly contact his or her eye care professional.
- Patients should be instructed not to expose their contact lenses to water while wearing them. Water can harbor microorganisms that can lead to severe infection, vision loss, or blindness. If their contact lenses have been submersed in water when swimming in pools, lakes, or oceans, the contact lenses should be discarded and replaced with a new pair. Recommendations for wearing lenses during any water activity should be discussed with the patient.

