## ADVERSE REACTIONS

The subject should be informed that the following problems may occur:

- Eyes stinging, burning, itching (irritation), or other eye pain,
- Comfort is less than when lens was first placed on eye,
- Abnormal feeling of something in the eye (foreign body, scratched area),
- Excessive watering (tearing) of the eyes,
- Unusual eye secretions,
- Redness of the eyes,
- Reduced sharpness of vision (poor visual acuity),
- Blurred vision, rainbows, or halos around objects,
- Sensitivity to light (photophobia),
- Dry eyes.

If the subject notices any of the above, he or she should be instructed to:

- **Immediately remove lenses.**
- If the discomfort or problem stops, then look closely at the lens. If the lens is in any way damaged, do not put the lens back on the eye. Place the lens in the storage case and contact the eye care professional. If the lens has dirt, an eyelash, or other foreign body on it, or the problem stops and the lens appears undamaged, the subject should insert a new lens. After insertion of a new lens, if the problem continues, the subject should **immediately remove the lenses and consult the eye care professional.**

If the above symptoms continue after removal of the lens, or upon insertion of a new lens, the subject should **immediately remove the lenses and contact his or her eye care professional** or physician, who must determine the need for examination, treatment, or referral without delay.

(See Important Treatment Information for Adverse Reactions.) A serious condition such as infection, corneal ulcer, corneal vascularization, or iritis may be present, and may progress rapidly. Less serious reactions such as abrasions, epithelial stinging or bacterial conjunctivitis must be managed and treated carefully to avoid more serious complications.

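### The written Subject Instructions give two incompatible directions for the same symptoms, and their text on damaged lenses, water, aerosols, stuck lenses and rewetting drops does not agree with the rest of the protocol

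*Protocol*

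**What the plan says.** **Symptoms.** Appendix C section 4 lists ten problems, among them pain, redness, light sensitivity and blurred vision, and has the subject take the lenses out at once. If the trouble settles, the subject looks at the lens. For an intact lens the direction reads, in part, "the problem stops and the lens appears undamaged, insert a new lens", and the study doctor is consulted if the problem goes on with the new lens. The closing paragraph warns that a serious condition may be present when any of these problems arises, and adds: "You should keep the lens off your eye and seek immediately professional identification of the problem and prompt treatment to avoid serious eye damage". Section 2 (Warnings) tells a subject with discomfort, tearing, a change in vision or redness to remove the lenses and contact the study doctor promptly.

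**Damaged lens and water.** The Fitting Guide (Appendix D, Adverse Reactions) says "If the lens is in any way damaged, do not put the lens back on the eye. Place the lens in the storage case" and then has the subject contact the professional. Its Warnings say "Patients should be instructed not to expose their contact lenses to water while wearing them", citing infection and loss of sight. Appendix C section 3 says only "Ask your study doctor about wearing lenses during water activities and other sports".

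**Stuck lens and drops.** Appendix C section 3 and the sticking-lens paragraph of section 5 tell the subject to "use a solution intended to lubricate or rewet a contact lens, as recommended by your eyecare practitioner", and not to take the lens out unless the study doctor advises it. Appendix C, General Information, bars products that were not dispensed, "with the exception of rewetting drops if you habitually use them". Protocol 4.5 sets the same limit, while the synopsis refers to eye drops that may be provided. At the 1-Week and 3-Week Visits (5.1.2 and 5.1.3) the drop-use item is marked "Only to be completed by subjects reporting rewetting drop use with habitual lenses at the Dispensing Visit". SAP 6.5.8 summarises drop use for baseline users only.

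**The concern.** Between visits, the site learns of an ulcer, an infiltrate or a faulty lens largely because the subject calls. The expedited clocks in Protocol 6.2.1 (serious events) and 6.2.3 (device deficiencies) are 24 hours from the site's awareness, so a subject left unsure whether to call can delay both care and reporting. The Fitting Guide itself notes that a minor abrasion and an early infected ulcer can look alike at first. Protocol 4.3.2 requires subjects to comply with the handout and provides for discontinuation in serious cases of non-compliance, yet compliance cannot be judged against text that points two ways.

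There is also a smaller data question. If a subject who did not use drops before the study starts using them on the study lens, the two scheduled follow-up visits do not ask about it.

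**Working it through.** No arithmetic applies, and the plan states no figure on this point. The check sets the current passages side by side.

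1. **Within Appendix C section 4.** Take a subject whose redness clears on removal and whose lens looks intact. The re-insertion step says to put in a new lens and consult only if the problem continues. The closing paragraph covers the same list, has no requirement that the symptom persist, and says to keep the lens off and seek help. Both cannot be followed.

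2. **Section 2 against section 4.** All four symptoms in section 2 have counterparts in the section 4 list. Section 2 agrees in substance with the closing paragraph of section 4 and has no re-insertion step. The two sections cannot be read as serving different situations, because General Information sends a symptomatic subject to both.

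3. **Appendix C against Appendix D.** The Fitting Guide opens its urgent step with a condition: symptoms that continue after removal or on insertion of a new lens. Appendix C carries the new-lens half of that condition in its re-insertion step, but the closing paragraph has no such lead-in. The Fitting Guide is not a clean reference either. Its own Warnings ask for removal and prompt contact without condition, which is the same tension.

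4. **Written omissions and differences.** The Fitting Guide's damaged-lens sentence has no counterpart in the matching step of Appendix C, which covers only a lens with a foreign body or one that looks intact. The water-exposure warning is absent from Appendix C section 2. On aerosols, Appendix C section 1 forbids use while lenses are worn, whereas the Fitting Guide's Precautions allow for use with care.

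5. **Stuck lens.** Section 4 orders immediate removal for any listed symptom. Section 3 and the sticking-lens paragraph forbid removal without the doctor's advice. No exception links them. The two appendices agree with each other on stuck lenses, so this conflict lies inside Appendix C.

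6. **Drops.** Any subject with a stuck lens is sent to a rewetting solution. General Information and Protocol 4.5 confine drops to habitual users, and Appendix C lists only lens cases as study products for the subject. The synopsis wording leaves it unclear whether drops are supplied. Appendix C section 1 allows drops that the study doctor has specifically approved, which the other passages do not mention.

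7. **Drop data.** The scheduled visits ask baseline users only (5.1.2, 5.1.3, and footnote a of the schedule in Appendix A and SAP Table 1). The Unscheduled Visit (5.1.5) asks without that limit, but SAP 6.5.2 restricts compliance summaries to scheduled visits. New use reported at an unscheduled visit would therefore reach listings and not the summary.

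**The case against.** Much can be said for the existing text. Every version begins with removal, and re-insertion means a new lens after the problem has stopped. Appendix C tells subjects to keep all worn lenses, bring them to each visit and call the study doctor with any problem. Lenses are replaced at every removal, so putting a damaged one back is already excluded. Protocol 4.3.2 requires the site to go through precautions and warnings with each subject, and the Fitting Guide tells the professional to give the water warning. The stuck-lens passages can be read as a specific exception to general removal, and the practitioner's recommendation offers a route to drops. Asking only habitual users about drops follows from the limit in 4.5, and drop use is not a listed efficacy or safety variable in SAP 6.4.

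These points narrow the concern without removing it. A reader might infer that a subject with a damaged lens has no direction or no route to the site. The general call-and-return instructions rule that out, and only the explicit sentence is missing. A reader might count three competing rules for symptoms, but section 2 and the end of section 4 are essentially one action, so there are two. A reader might infer that subjects are certainly given no drops, or that new drop use is wholly invisible. The synopsis wording, the Unscheduled Visit form and the listing of deviations do not support either. What stands is that the written text contradicts itself, and that the stuck-lens exception is nowhere stated.

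**Conclusion.** The point holds as a defect in the written instructions. Section 4 of Appendix C gives two incompatible directions for one symptom list. The damaged-lens step and water warning are missing from the subject's text, the aerosol wording differs between the appendices, and the stuck-lens advice conflicts with both the removal order and the drop restriction. Every subject is to receive the handout, approximately 300 by plan. The number who would meet one of these situations, or who would start drops on the study lens, cannot be derived from the documents; a count of baseline non-users would not measure it.

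The conclusion assumes that the handout is used as printed. Oral advice at the site and the consent form, which was not available for this review, may fill some gaps. The sample size, primary endpoint and error rate are unaffected. The rewetting-drop data gap is a separate, minor point.

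**What to change.** The sponsor should reconcile Appendix C sections 2, 3 and 4 and the sticking-lens paragraph with each other; with the synopsis, Protocol 4.5, and Appendix C General Information and section 1; and with the Fitting Guide's Warnings, Precautions and Adverse Reactions. Each situation should end with one consistent written instruction: symptom stops, symptom continues, damaged lens, stuck lens, water exposure, aerosols, and who may use drops. The sponsor's clinical team decides which rule applies in each case. This review does not propose one and does not treat the Fitting Guide as the correct version.

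Separately, remove the skip rule in 5.1.2 and 5.1.3 so that rewetting-drop use is recorded for all subjects at both follow-up visits, align footnote a in Appendix A and SAP Table 1, and change SAP 6.5.8 to summarise it for all subjects.

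The cost is a document revision with IRB approval before use, one eCRF skip rule and a short SAP edit. No new procedure or visit is needed.
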